Speech Adaptation When Using Mouthguards

Research Protocol

4 October 2017

Table of content

	Page
Introduction	3
Problem Statement	4
Research Questions	4
Hypothesis	4
Aim and Objectives	5
Methodology	5
Flow Chart of Methodology	11
References	13

1. Introduction

Contact sports are defined as sports in which players interact with each other, trying to prevent the opposing team or player from winning (Barbic et al., 2005). Thus, participation in sports carries a considerable risk for dental injuries (Sane, 1998.) Due to the unavoidable repeated bodily contact, dental trauma highly prevalent among rugby players (Abdullah et al., 2015). The prevalence and severity of sport-related dental injuries varied, with an estimate between 0.2% and 33.5%, but is likely to be underreported (Cohenca et al., 2007). The risk of injuries increased with the age of the players, especially among those involved in long hours of training and compete professionally (Turbeville et al., 2003).

Dental trauma often involves injuries to the tooth structure, periodontal tissue, oral mucosa and temporomandibular joints (Feliciano, 2006). The vulnerable site is the upper jaw, particularly upper incisors (Glendor, 2008). These injuries often affect the appearance of the casualties, causing undue psychological stress (Berger, 2009). Furthermore restoring the injured teeth often requires extensive dental procedure with long-term follow-up at a high cost (Glendor, 2001). Thus, familiarity with the emergency procedure for dental trauma was essential for improving the condition of the affected tooth. However, knowledge of dental trauma prevention and management were generally insufficient, suggesting the need to educate and train the athletes (Abdullah et al., 2015).

Mouthguards are typically composed of a thermoplastic copolymer, designed to fit over the occlusal surfaces of the maxillary teeth and extending near to the vestibular reflection (Patrick et al., 2005). Several authors demonstrated that wearing a mouthguard during sport can reduce the occurrence and severity of dental trauma (Yesil et al., 2009). Therefore, some sports authorities mandate the use of mouthguard (Quarrie et al., 2005). The purpose of using a mouthguard is to act as a buffer from trauma and provide a degree of protection for both the mouth's soft tissues (lips, gums, tongue) and hard tissues (teeth and alveolar bone) as well as protection from brain injuries (Knapik et al., 2007). The ability to protect the mouth is highly dependent on the ability of the mouthguard in shock absorption and impact dissipation (Craig et al., 2002).

There are basically three types of mouthguards that are available in the market. Type I (stock) are sold to the public and are used without any modification. Type II ('boil and bite') mouthguards are the most commonly used mouthguards on the market and represent 90% of all mouthguards worn (Padilla et al., 1996). These are made of a thermoplastic material that is softened and then molded to the dental arch by the user. Type III (custom-made) are made by a dentist using a mold of the patient's dental arches (Barbic et al., 2005).

Rugby is contact sports that need good physical fitness skills and specific skills depending on the position played. The team that can quickly and efficiently communicate during a rugby game has a clear advantage. Thus, building good on-field communication habits make much easier for rugby players to work together. However, if the communication fails during rugby games, the prospect of success in offense and defense during rugby games will be greatly decreased (Gordon, 2005). Among Malaysian university rugby players, those who discontinued using mouthguard complaint that general discomfort and speech disturbance are the main barriers to compliance (Liew et al., 2014). The nuisance is largely due to their use of poorly-fitted stock or boil-and-bite mouthguards (Liew et al., 2014). In comparison, custom-fitted mouthguards were considered the best choice because of its ability to maintaining oral moistness and adaptation, hence causing less interference with respiration and speech, while improving comfort and limiting nauseating effect (Duarte-Pereira et al., 2008). However, limited availability and higher prices hinder its widespread use (Guevara et al., 2001).

To date, the intensity and duration of oral discomfort caused by mouthguard remain unclear, with no published study to evaluate speech performance that employed acoustic analysis and sonography. Hence, the aim of this research is to evaluate the impact of wearing mouthguards on the speech performance of the athletes.

2. Problem Statement

Rugby exposes players to increased risk of dental trauma. Thus, mouthguard use is often recommended. However, a mouthguard can affect speech. It is unclear to what extent speech performance improve over time.

Therefore, this project is intended to evaluate the impact of wearing mouthguards on the speech performance of the players. In addition, the effectiveness of custom-fitted mouthguards in the prevention of dental trauma could be evaluated.

3. Research Question

- i. Is there any difference in speech performances before (at baseline), immediately after, one-week after, one-month after and six-month after wearing a custom-fitted mouthguard?
- ii. Is there any difference in the level of oral impairment immediately after, one-week after, one-month after and six-month after wearing a custom-fitted mouthguard?
- iii. What is the incidence of traumatic dental injury among rugby players during the six-month period of wearing a custom-fitted mouthguard?

4. Aim and Objectives

The aim of this study is to evaluate the effect of wearing custom-fitted mouthguards on the speech performance and oral impairment of the Malaysia national rugby players.

The specific objectives are :

- i. To compare the speech performance before, immediately after, one-week after, one-month after and six-month after wearing custom-fitted mouthguard;
- ii. To compare the level of oral impairment before, immediately after, one-week after, one-month after, and six-month after wearing custom-fitted mouthguard; and
- iii. To estimate the incidence of traumatic dental injury within the six-month custom-fitted mouthguards use period.

5. Research hypotheses

The null hypotheses are :

- i. Speech performance at various time points is not affected by wearing custom-fitted mouthguard;
- ii. Level of oral impairment at various time points is not affected by wearing custom-fitted mouthguard; and
- iii. No incidence of dental trauma occurs within the six-month custom-fitted mouthguards use period.

6. Methodology

An interventional study using single-arm pre- and post- design will be carried out at the National Sports Institute. All the national rugby players taking part in the Asia Rugby Championship Premier 2018 will be invited to participate in this study. The information sheet regarding the study will be given out while the objectives and conduct of the study will be explained to the players. All players who agreed to participate will need to provide written informed consent.

To be eligible for inclusion, the players must be:

- a) Men aged between 18 and 35;
- b) Actively playing rugby;
- c) Currently playing in Malaysia Rugby Union;
- d) Native speakers of Malay (national language), with the ability to read and write in Malay fluently;
and
- e) Without any history of either speech or hearing impairment.

The exclusion criteria are:

- a) Retired players;
- b) National players who did not play rugby within the last six months of the recruitment date; and
- c) Players with cleft lip and/or cleft palate; and

d) Players with any history of either speech or hearing impairment.

The sample size was calculated using G*Power 3.1 software (available at <http://www.gpower.hhu.de/>). The assumptions was an effect size of 0.25 with a 5% margin of error. The power of the study 80% and there was a total of six repeated measurements. Correlation among the repeated measures was set at 0.5. This yielded a minimal sample size of 24. Considering that drop-outs are higher with long-term follow-up, the sample size was increased by 20% to $n = 30$.

Development of questionnaire to evaluate oral impairment

A questionnaire will be developed to evaluate any oral impairment that could be experienced by the subjects before and during the use of a mouthguard. The questionnaire will be divided into four parts: (i) demographic information such as gender, age, frequency and duration of playing, highest level of representation and experience wearing custom-fitted mouthguard, (ii) frequency of wearing mouthguard, (iii) problems arise during mouthguard use and (iv) general perception on mouthguard. All questions in part (ii), (iii) and (iv) will be formatted in a five-point Likert scale. The following ratings will be given for the different possible answers in part (ii) and part (iii) with a qualitatively ordinal character: “Never” = 1; “Rarely” = 2; “Sometimes” = 3; “Often” = 4; “Always” = 5. For part (iv), the possible responses were: “Strongly disagree” = 1; “Disagree” = 2; “Neutral” = 3; “Agree” = 4; “Strongly agree” = 5. The questionnaires will be printed in Malay, the national language of Malaysia.

This questionnaire set will be validated and pretested on 10 undergraduate dental students. The cognitive interview will be carried out while the students are completing the questionnaire. Face validity will be determined as the degree to which they agree that the items of the questionnaire are appropriate and adequate to measure pattern and problems of wearing the mouthguard, as well as the general perception on the mouthguard.

Fabrication of mouthguards

Dental impressions of the upper-jaw of all of the subjects will be taken using alginate impression material and rigid perforated stainless-steel trays. The impressions will be rinsed under running tap water before spraying with disinfectant. The impressions will be transported in sealed and labeled zip-lock bags. The impressions will be cast within the same day using Type II dental stone. After the model hardens, usually about 45 minutes, the highest margins of the vestibular border will be marked with a pencil for reference during trimming. At the model trimmer, the excess stone will be carefully removed.

Pressure dual laminated technique will be used by technicians to fabricate the mouthguards. Ethylene-vinyl acetate (EVA) thermoplastic sheets of 3 mm in thickness with 125 mm diameter (Dentsply International Raintree Essix, Court East Sarasota, USA) will be used. The first layer of white EVA sheet will be adapted on the model and heated under pressure in the thermo-pressure machine (Erkopress 300 Tp by Erkodent, Germany). The first layer will be allowed to cool down at room temperature for a minimum of 10 to 15 minutes and excess material will be trimmed. The second layer of black EVA sheet will then be adapted on top of the first layer using the thermo-pressure machine. The mouthguard will further be trimmed and smoothed to the desired thickness. Two 3 mm sheets laminated together should form an even thickness of 4 mm mouthguard. An Iwanson spring wax calipers crown gauge measuring 1-10 mm calibrated scale will be used to ensure all mouthguards constructed had uniform 4 mm thickness at occlusal, buccal and palatal surfaces. The design of the mouthguards takes into consideration of the following limits: (i) the labial borders of the mouthguard were extended to within 2 mm of the vestibular reflection, (ii) the palatal margins were trimmed to the cervical area of the palatal surface of the upper teeth, (iii) enclosing the maxillary teeth to the distal surface of the first molars. The adaptation, stability, and retention of the mouthguards will be checked when it is delivered to the players. Adjustments will be performed when necessary. Any complaint of sharp edges will be handled. The players will be instructed on the use and care of the mouthguards.

Speech performance measurement

Prior to the fitting of the mouthguard, speech samples will be recorded from each participant. These speech samples were used as control (T₀). The recording of speech samples will be performed using the Sony IC Recorder (ICD-SX700/SX800, San Diego, USA) in a quiet room to minimize background sound. The recorder will be placed 15 cm away from the player's lips and each player will be asked to read loudly a list of selected Malay words (*paku* for phoneme /p/, *bola* for phoneme /b/, *tatu* for phoneme /t/, and *dadu* for phoneme /d/), as the words are shown one after another on the computer screen. Each session will take about 10-20 minutes to complete. Three recordings will be obtained for each word. The mouthguard will then be fitted for each player. The recording of speech samples will be repeated immediately following wear (T₁), and at the following intervals: one-week after (T₂), one-month after (T₃) and six-month after wear (T₄).

Evaluation of oral impairment and compliance

Before the mouthguard is fitted, all participants will be asked to fill up the questionnaires (at T₀). They will also be requested to fill up the same questionnaire at the same time points prior to the recording of the speech samples at T₁, T₂, T₃, and T₄.

Compliance and injury monitoring

Throughout the six-month period, the compliance of wearing mouthguards and the occurrence of dental trauma during training will be monitored on-site by the researcher or if not available, an assigned coach. A 24-hour helpline will be provided as a surveillance tool to monitor problems with mouthguards and dental trauma. Besides, replacement mouthguard will be provided for only once, if the players damage or misplace the mouthguard. However, if the players damage or misplace the mouthguard more than two times, they will be withdrawn from the research.

Data analysis

Data collected from the questionnaires will be analyzed using SPSS version 23.0 (IBM Corporation, Armonk, NY, USA). Descriptive analysis will be performed for demographic data to have an overview of the participants' age, frequency, and duration of playing and experience of wearing a custom-fitted mouthguard.

[figure not shown]
For the self-assessment questionnaire of oral impairment, Friedman's test will be used to test for differences between groups because the dependent variable being measured is ordinal. Statistical significance is set at $\alpha = 0.05$. Subsequently, the Wilcoxon signed-rank test will be used for pairwise comparison. Bonferroni adjustment will be done to correct for multiple testing. For part (ii) self-reported frequency of wearing custom-fitted mouthguards, comparisons will be made between T₂, T₃, and T₄. Hence, the adjusted level of statistical significance is set at $\alpha = 0.05/3 = 0.017$. For (iii) problems arise during mouthguard use, and (iv) general perception on a mouthguard, the level of statistical significance is adjusted to $\alpha = 0.05/6 = 0.008$ because of multiple testing between T₁, T₂, T₃, and T₄.

All the recorded speech waveforms will be digitized (at a sampling rate of 22 kHz and 32-bit resolution) and stored on a compact disk. The speech samples collected will be transcribed into the PRAAT software version to assess the acoustic characteristics of the sound via spectrographic analysis. Each speech sample file was given a number which referred to a participant's profile to blind the assessor.

By using spectrogram analysis, mean voice onset time (VOT) values for all phonemes */p b t d /* will be measured in a millisecond. The measurements will be done by manually positioning two cursors in the display of the waveform/spectrogram in the sample file. The beginning and end of a particular measurement of a sound will be judged from both the waveform and spectrogram. The average mean VOT values and voicing duration from the three readings will be obtained for each phoneme.

One-way repeated-measures analysis of variance (ANOVA) will be used to compare the VOT of each phoneme at different time intervals (T_0 , T_1 , T_2 , T_3 , T_4). Statistical significance is set at $\alpha = 0.05$.

7. Flowchart of the study

6 month monitoring period

1. Monitoring logbook
2. 24-hour helpline
3. Modification/replacement of mouthguards (if necessary)

Fourth Speech Performance Recording (T₃)

Fourth Questionnaire Oral Impairment Survey
(T₃)

8. References

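### Null hypothesis iii asserts zero dental trauma where objective iii asks for an incidence estimate; no trauma analysis is planned, and active monitoring is worded for training only

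*Combined protocol and SAP*

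**What the plan says.** Three statements concern dental injury. Section 3, question iii, asks "What is the incidence of traumatic dental injury among rugby players during the six-month period of wearing a custom-fitted mouthguard". Section 4, objective iii, is "To estimate the incidence of traumatic dental injury within the six-month custom-fitted mouthguards use period". Section 5, null hypothesis iii, reads "No incidence of dental trauma occurs within the six-month custom-fitted mouthguards use period".

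The Data analysis part of section 6 covers demographics (descriptive), questionnaire parts ii to iv (Friedman, then Wilcoxon with Bonferroni adjustment) and voice onset time (repeated-measures ANOVA). Dental trauma does not appear there.

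On ascertainment, Compliance and injury monitoring says that "the occurrence of dental trauma during training will be monitored on-site by the researcher or if not available, an assigned coach". It also provides a 24-hour helpline for mouthguard problems and dental trauma. The flowchart in section 7 lists a monitoring logbook but, in the text available, does not say what is entered in it. The questionnaire is described in four parts, and none is described as asking about injury.

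On follow-up, the sample size paragraph allows for drop-out (24 raised to 30), and a withdrawal rule applies: "if the players damage or misplace the mouthguard more than two times, they will be withdrawn from the research". How the injury data of players who leave early will be counted is not stated.

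**The concern.** An estimation objective and a null of exactly zero are different kinds of statement. A single injury disproves the null and says nothing about how large the incidence is. An absence of injuries invites the report that null iii was upheld, although a sizeable risk outside this cohort could remain. With no trauma analysis written down, nothing in the plan obliges the report to show that uncertainty.

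The count itself may also be incomplete. Active observation is worded for training, while match injuries may come to light only if someone reports or logs them. If some are missed, a low or zero count becomes more likely, and that is the result most easily misread under null iii.

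**Working it through.** **1. The plan's own figures.** The documents give no expected incidence, precision or power for trauma. The sample size paragraph gives 24, raised to 30, and 24 / (1 − 0.20) = 30. I take 24 and 30 as given and use them as the two plausible numbers of players. How 24 was obtained does not bear on this point.

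**2. Null iii treated as a test.** If the true risk is p = 0, no event can occur. The rule of rejecting at one or more injuries then has type I error 0, and one injury refutes the null with certainty. In the other direction, P(no player injured) = (1 − p)^n. For n = 30 and assumed risks:

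- p = 1%: 0.99^30 = 0.74
- p = 5%: 0.95^30 = 0.21

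A zero count is therefore unsurprising under risks well above zero.

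**3. Exact 95% intervals (Clopper-Pearson).** The counts are assumed, and players are treated as independent and as a sample of rugby players. For 0 of n the upper limit is 1 − 0.025^(1/n). For 1 of n the limits are the 2.5% quantile of Beta(1, n) and the 97.5% quantile of Beta(2, n − 1).

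| Injured / players | Estimate | 95% interval |
|---|---|---|
| 0 / 30 | 0% | 0 to 11.6% |
| 0 / 24 | 0% | 0 to 14.2% |
| 1 / 30 | 3.3% | 0.1 to 17.2% |
| 1 / 24 | 4.2% | 0.1 to 21.1% |

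**4. Effect of the denominator alone.** One injury is 1/30 = 3.3% of players fitted or 1/24 = 4.2% of completers, a difference of under one percentage point. With no injuries there is no difference.

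**5. Effect of unknown injury status.** Assume 30 are fitted and 6 leave early with status unknown, in line with the drop-out allowance. With no recorded case the possible range is 0/30 to 6/30, or 0 to 20%. With one recorded case it is 1/30 to 7/30, or 3.3 to 23.3%. These are extreme bounds: the upper ends need every early leaver to have had an unrecorded injury. They come from an uncertain numerator, not from the choice of denominator.

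**6. Person-time.** Complete follow-up of 30 players gives 30 × 6 = 180 person-months. With no events the exact Poisson upper limit is −ln(0.025) / 180 = 3.689 / 180, or 2.05 per 100 person-months. With one event the rate is 1/180 = 0.56 per 100 person-months (95% interval 0.01 to 3.10).

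**7. Ascertainment.** No arithmetic applies. The on-site sentence names training. The helpline sentence is not limited to training but depends on someone calling. The scope of the logbook cannot be determined from the available text. The size of any under-count cannot be calculated.

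**The case against.** The strongest reply is that null iii does no work. It has no test, alpha or decision rule, so nothing in the plan would formally uphold it. It can also be read as a statement about this squad: the aim names the Malaysian national players, and all those in the 2018 championship are invited. On that reading the observed count is the answer and no interval is needed. Part of this stands. The intervals above are conditional on treating the players as a sample. Question iii, however, speaks of rugby players without that restriction. Even for a complete squad, a null of zero is not what the objective asks for, and the trauma analysis is still absent.

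It is also fair to say that the missing estimator and case definition would, taken alone, be gaps of detail, and that the denominator matters little (step 4).

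Four stronger readings are tempting and are not supported:

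- **That match injuries will be missed.** The helpline or the logbook may capture them, and the flowchart is incomplete in the available text, so the logbook's scope cannot be held against the plan.
- **That the choice of denominator could move the result by 20 percentage points.** The wide bounds in step 5 describe unknown injury status at its extreme.
- **That 11.6% can be set against the Introduction's range,** "with an estimate between 0.2% and 33.5%, but is likely to be underreported". That range refers to prevalence and severity of sport-related dental injury, not to six-month incidence in mouthguard wearers, so the comparison is not like for like.
- **That the study will claim protection from a zero count.** The Problem Statement mentions evaluating preventive effectiveness, but no objective or analysis takes this up.

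**Conclusion.** The point holds as a minor one. Null iii does not match objective iii or question iii, and it cannot be supported by any result this study can produce. Data analysis has no entry for trauma. If no injury is recorded, a risk of up to 11.6% (30 players) or 14.2% (24 players) stays compatible with the data, provided the players are regarded as an independent sample of rugby players. Under-counting of match injuries is a risk that follows from the wording of the monitoring paragraph; it is not shown to occur and cannot be quantified. Incidence is the third, descriptive objective and the sample size is not based on it. The speech and questionnaire analyses are unaffected.

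**What to change.** 1. Delete null hypothesis iii and keep objective iii as worded. Add to Data analysis: the number of players with at least one dental injury over all players fitted with a mouthguard, with an exact (Clopper-Pearson) 95% interval. State how many had incomplete follow-up. Add a rate per person-month, because counting early leavers only to last contact treats their unobserved time as injury-free and biases the proportion downward. If bounds for unknown injury status are reported, label them as extreme.

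2. At T2, T3 and T4, and at last contact for anyone leaving early, ask every player about any dental injury since the last visit, in training or match.

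The cost is a few lines of protocol text and one question at three visits already scheduled, plus a last contact for early leavers. There are two downsides. The question relies on recall, over the longest gap between one and six months. The interval will stay wide, because neither change adds players or follow-up time.

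### The single 80% power figure comes from a parametric six-measurement calculation; the plan has five time points, and the Friedman tests for objective ii fall short of 80% at the 24 completers planned for

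*Combined protocol and SAP*

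**What the plan says.** The sample-size paragraph (section 6, Methodology) gives one G*Power calculation. On effect size and alpha it says: "The assumptions was an effect size of 0.25 with a 5% margin of error". On the target power and the count of visits it says: "The power of the study 80% and there was a total of six repeated measurements". On the correlation it says: "Correlation among the repeated measures was set at 0.5". The result is: "This yielded a minimal sample size of 24". The final figure, 30, comes from a drop-out allowance, introduced by: "Considering that drop-outs are higher with long-term follow-up, the sample size was increased by 20% to".

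The aim in section 4 is to "evaluate the effect of wearing custom-fitted mouthguards on the speech performance and oral impairment of the Malaysia national rugby players". Each of the two has its own objective and null hypothesis, and no primary outcome is named.

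The Data analysis text treats the two outcomes differently.

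- Voice onset time (VOT) is compared over T₀ to T₄ by one-way repeated-measures ANOVA.
- For the questionnaire, "Friedman's test will be used to test for differences between groups because the dependent variable being measured is ordinal", at alpha 0.05, followed by Bonferroni-adjusted Wilcoxon tests.
- For part (ii), frequency of wear, "comparisons will be made between T₂, T₃, and T₄" (three pairs, 0.017). For part (iii), problems during use, and part (iv), perception, the set is T₁ to T₄ (six pairs, 0.008).

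No power is given for Friedman's test, and no analysis in the plan has six measurements.

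**The concern.** Because the 80% is attached to the study as a whole, a reader will take it to cover objective ii. Two features of the questionnaire analysis reduce power below that figure. Fewer visits enter the test than the six assumed, and Friedman's test ranks only within a player, which costs efficiency when there are few visits.

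Null hypothesis ii is that oral impairment is not affected. Section 1 reports discomfort and speech disturbance as the main reasons players give up mouthguards. If a non-significant Friedman result is read against a claimed 80% power, it will look more reassuring than it is.

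**Working it through.** **Inputs.** From the sample-size paragraph: f = 0.25, alpha = 0.05 (reading the 5% margin of error as alpha), correlation ρ = 0.5, m = 6, target power 0.80, N = 24, then 30. The drop-out step is 24/0.8 = 30 (24 × 1.2 = 28.8 would round up to 29), so the plan itself provides for 24 completers.

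**Reproducing the plan's figure.** The noncentrality is λ = f²·N·m/(1 − ρ), for one group.

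- MANOVA form, df = m − 1 and N − m + 1. At m = 6, N = 24: λ = 0.0625 × 24 × 6/0.5 = 18, df 5 and 19, power 0.825. At N = 23 power is 0.799. The minimum is therefore exactly 24.
- Univariate ANOVA under sphericity, df = m − 1 and (N − 1)(m − 1). At m = 6 the minimum is 19, and N = 24 gives 0.913. This form yields 24 only if an input differs from those stated, for example a sphericity correction of about 0.7, 90% power, or m = 4.

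The protocol does not name the test, so the MANOVA origin is an inference from this match.

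**VOT as planned.** Five time points, N = 24: λ = 0.0625 × 24 × 5/0.5 = 15. Univariate (df 4 and 92) power is 0.873. Multivariate (df 4 and 20) power is 0.797.

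**Friedman's test, same f, ρ and alpha.** Two methods were used.

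1. Multiply λ by the asymptotic relative efficiency under normality, (3/π)·m/(m + 1), keeping the univariate df. With N = 24:
   - m = 3: 9 × 0.716 = 6.45, power 0.587
   - m = 4: 12 × 0.764 = 9.17, power 0.693
   - m = 5: 15 × 0.796 = 11.94, power 0.776
2. Simulate 20,000 trials per cell. The latent response is the sum of a visit effect (SD 0.25), a player effect (variance 0.5) and error (variance 0.5), under several mean profiles. The tie-corrected statistic is compared with the chi-square critical value. Responses are taken as continuous, cut into five equally likely categories, or cut into five categories skewed towards the lowest answer.

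| Completers | Visits | Continuous | Five-point, even | Five-point, skewed |
|---|---|---|---|---|
| 24 | 3 (T₂–T₄) | 0.60–0.61 | 0.59 | 0.52–0.55 |
| 24 | 4 (T₁–T₄) | 0.69 | 0.67 | 0.60–0.64 |
| 24 | 5 (T₀–T₄) | 0.77 | 0.74–0.75 | 0.66–0.71 |
| 24 | 6 (not in plan) | 0.82–0.83 | 0.78–0.80 | 0.72–0.78 |
| 30 | 3 | 0.71–0.72 | 0.70 | 0.63–0.66 |
| 30 | 4 | 0.80 | 0.78 | 0.71–0.75 |
| 30 | 5 | 0.87 | 0.84–0.85 | 0.78–0.83 |

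Repeat simulations with other cut-points widen these ranges slightly. At 24 completers, four visits without skew span about 0.66 to 0.70, and three visits with skew go down to 0.51. At 30, four visits without skew span about 0.78 to 0.81.

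The six-visit row is informative: with six visits a Friedman test on continuous data would have reached 80%. The shortfall comes from combining fewer visits with within-player ranking. Over four visits at N = 24, the univariate ANOVA would have 0.817 against 0.69 for Friedman.

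**The case against.** Several points on the other side carry weight.

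*Speech is the lead outcome.* The title says so, and the Introduction and Problem Statement describe the aim as speech performance. Sizing a study on its lead outcome, without 80% power for every secondary item, is ordinary practice. That stands, and it is why no extra players are asked for. But the sample-size paragraph does not limit its claim to speech, and section 4 gives oral impairment equal standing.

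*The visit sets are named only for the pairwise tests.* This is correct. T₂–T₄ and T₁–T₄ appear where the Bonferroni divisors are set, and no visit set is given for the Friedman test itself. Objective ii includes the period before wear, and questionnaires are completed at T₀, which supports five visits; research question ii omits baseline. With five visits the unskewed shortfall at 24 completers is only 3 to 6 points.

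*The effect size is not a Friedman input.* Placing f = 0.25 on a latent normal scale, and holding it fixed for three, four or five visits, is an assumption. So are compound symmetry and the cut-points. The documents do not say whether items are tested singly or summed. The Friedman figures are therefore conditional, although every configuration with the plan's own visits falls below 0.80 at 24 completers.

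A reader might infer two stronger things. One is that the oral-impairment test has only about 60% power, so that a real effect is missed twice as often as the plan implies. That figure belongs to part (ii), frequency of wear, which is a compliance measure and not the level of oral impairment in null hypothesis ii. The other is that the plan will take a non-significant result as proof of no effect. No section says so; the nulls in section 5 are ordinary null hypotheses.

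**Conclusion.** The point holds as a matter of what the 80% covers and of a wrong measurement count. The stated N is not miscalculated: 24 reproduces. It does so, however, for a six-measurement parametric test, whereas the plan has five time points and a rank test for objective ii.

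For parts (iii) and (iv) at 24 completers, Friedman power is about 0.66 to 0.70 over T₁–T₄ (0.60 to 0.64 if skewed), or about 0.74 to 0.77 with T₀ included (0.66 to 0.71 if skewed). Without skew, the chance of missing an effect of the assumed size is thus about 30–34% over four visits, or 23–26% over five, against the stated 20%. Part (ii) has about 0.60 (0.51 to 0.55 if skewed) and stays below 0.80 even if all 30 complete. With 30 completing and no skew, parts (iii) and (iv) come to roughly 80% over four visits and exceed it over five.

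These figures concern the overall Friedman test at 0.05, before any pairwise correction. They rest on a normal latent response, compound symmetry, f = 0.25 on that latent scale, and assumed category cut-points. The VOT analysis is not in question under sphericity.

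**What to change.** In the sample-size paragraph:

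- Correct the number of repeated measurements from six to five.
- Say that the calculation applies to the repeated-measures ANOVA of VOT (objective i), and give its power at 24 completers: 0.87 univariate under sphericity, 0.80 multivariate. Remove the attribution of power to the study as a whole.
- State that objective ii is not powered at 80% at 24 completers. Give the Friedman power as a range with its assumptions, not as a single settled value.

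In the Data analysis text:

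- State which visits enter each Friedman test, and reconcile this with objective ii (which includes baseline) and research question ii (which does not).
- State that a non-significant Friedman result will be reported as inconclusive.

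The cost is a few sentences and a less favourable stated power for objective ii. Enrolment, visits and tests do not change.
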